Clinical Trial Protocol: 15VR8

Date

Version 2: 30 June 2016
Version 1: 19 November 2015

Study Title: An Open-Label, Long-Term Extension Study of the Safety of Somavaratan (VRS-317) in Adults with Growth Hormone Deficiency (GHD)

Study Number: 15VR8
Study Phase: Open Label Extension
Product Name: Somavaratan (VRS-317)
IND Number: 108471
Indication: Adult Growth Hormone Deficiency
Investigators: Multicenter
Sponsor: Versartis, Inc. (Versartis)
Study Director: [REDACTED]
Versartis

Medical Monitor: [REDACTED]
Versartis

Global Project Manager: [REDACTED]
Premier Research

Study Statistician: [REDACTED]
Premier Research

APPROVAL/SIGNATURE PAGE: SPONSOR AND CONTRACT RESEARCH ORGANIZATION

Sponsor: Versartis, Inc.
[name]
[name]

Medical Monitor:

[Redacted]

Va

Signature: _____

[Redacted]

Date: _____

Clinical Operations:

[Redacted]

Versartis

Signature _____

[Redacted]

Date: _____

Contract Research Organization:

Premier Research
[name]
[name]
[name]

Project Manager:

[Redacted]

Premier Research

Signature: _____

[Redacted]

Date: _____

Project Statistician:

[Redacted]

Premier Research

Sign _____

[Redacted]

Date: _____

SYNOPSIS: PROTOCOL 15VR8

SPONSOR Versartis, Inc.
NAME OF FINISHED PRODUCT Somavaratan (VRS-317)
NAME OF ACTIVE INGREDIENT Somavaratan (VRS-317)
STUDY TITLE An Open-Label, Long-Term Extension Study of the Safety of Somavaratan (VRS-317) in Adults with Growth Hormone Deficiency (GHD)
STUDY NUMBER 15VR8
PHASE OF DEVELOPMENT Long-Term Extension Study
OBJECTIVE(S) The primary objective of this study is: 
• To evaluate the safety of somavaratan during long-term treatment in adults with GHD The secondary objectives of this study are: 
• To evaluate the dose (starting and maintenance) and the dose titration plan of twice-monthly somavaratan during long-term treatment• To evaluate the immunogenicity of somavaratan during long-term treatment in adults with GHD by detection of anti-somavaratan antibodies (anti-drug antibodies, ADAs)• To evaluate pharmacodynamic responses (IGF-I, IGFBP-3) during long-term somavaratan treatment
STUDY DESIGN General This open-label extension study will evaluate the safety of long-term twice-monthly administration of somavaratan in adults with GHD. This is an open-label, multicenter study open to subjects completing a Versartis adult GHD study as well as approximately 40 new somavaratan naïve subjects (either rhGH treatment naïve or currently receiving daily rhGH therapy). All subjects will receive twice-monthly (every 15 days \pm 2 days) subcutaneous (SC) somavaratan. Doses will be titrated to each subject's individual IGF-I responses based on the IGF-I level 7 days post-dose until a maintenance dose is achieved. Maintenance dose is defined as an IGF-I value between 0 and 2.0 SDS for two consecutive 7 day post-dose time points (Day 8, peak level). Subjects receiving somavaratan once-monthly in this study (Protocol 15VR8) or in a previous somavaratan study (Protocol 15VR7), will have their dose decreased by half (minimum dose of 20 mg, 40 mg for women on estrogen, rounded down to the nearest even number) and will be titrated per the Dose Titration Plan (Table 2). New subjects enrolling in this study will be assigned to one of two cohorts and will receive a starting dose of 20 mg twice-monthly (40 mg for women on estrogen) (Table 1) and will be

titrated per the Dose Titration Plan (Table 2). Maintenance doses may be adjusted further based on PD data at the discretion of the Investigator or Medical Monitor.

Table 1 Study Drug Starting Dose Information:

Subject Cohort Assignment	Fixed Starting Study Dose	Frequency of Administration
Cohort 1: Adults with GHD irrespective of age and gender	20 mg	Twice-Monthly
Cohort 2: Women receiving oral estrogens	40 mg	Twice-Monthly

Table 2 Dose Titration Plan

Downward Dose Titration		
IGF-I at Day 8	Cohort 1	Cohort 2
0 to 2.0 SDS	No change in dosing	No change in dosing
2.01 to 3.0 SDS	4 mg dose decrement	4 mg dose decrement
Greater than 3.0 SDS	10 mg dose decrement	10 mg dose decrement
Upward Dose Titration ¹		
IGF-I at Day 8	Cohort 1	Cohort 2
-1.0 to 0 SDS	4 mg dose increment	10 mg dose increment
Less than -1.0 to -2.0 SDS	10 mg dose increment	20 mg dose increment
Less than -2.0 SDS	20 mg dose increment	40 mg dose increment

1: Maximum allowable dose is 250.0 mg

Study in clinic visits/blood sample collections will occur every week for the first 4 weeks of the study, followed by monthly in clinic visits until the subject has reached maintenance dosing. Some of the blood sample collections may be obtained in the subject's home throughout the study. Somavaratan doses will be administered in clinic During Month 1 and at each monthly Day 1 visit until maintenance dosing is achieved. After Month 1, Day 16 doses may be administered at home. In clinic visits will occur quarterly during the first year. Although quarterly visits will continue throughout the study, after the first year blood samples will be collected every 6 months, with intervening visits used for brief physical exams and collection of AEs and concomitant medications.

A total of up to 250 subjects will be enrolled.

Safety

Subjects will be monitored for safety throughout their participation in the study. Safety will be monitored by physical examination, inspection of injection sites, vital signs, ECGs (new subjects only), and clinical laboratory determinations. Adverse events (AEs) and concomitant medications (CMs) will be captured. AEs will be graded using the Common Terminology Criteria for Adverse Events (CTCAE). AEs will be coded using the MedDRA dictionary and CMs using the WHO Drug Dictionary (WHODDE, WHO Drug Dictionary Enhanced).

For new subjects, electrocardiograms (12-lead ECGs, triplicate tracings) will be conducted at Screening and repeated at Day 1 and Month 4 at 3 days (± 1 day) after dosing.

An external data safety and monitoring board (DSMB) will monitor and protect the safety of the study subjects throughout the study duration. DSMB meetings will occur twice yearly (approximately every 6 months).

The Stopping Criteria for individual subjects include:

1. The Principal Investigator (PI) and/or Medical Monitor conclude it is unsafe or not in the subject's best interest to continue.
2. IGF-I SDS ≥ 3.0 SDS on two consecutive Day 8 time points despite dose adjustments.
3. IGF-I SDS ≥ 2.0 SDS on two consecutive Day 8 time points despite dose adjustments and accompanied by clinically meaningful drug-related AEs, as determined by the Investigator and the Medical Monitor.

Subjects meeting individual stopping criteria will be withdrawn from the study.

The Stopping Criteria for the study itself include the determination that the study is unsafe to continue.

Pharmacokinetics (PK) and Pharmacodynamics (PD)

The PK parameter is somavaratan concentration and the PD parameters are serum IGF-I and IGFBP-3. All subjects will have blood samples collected for PK/PD assessments at Day 1 (pre-dose) and Days 8, 16, and 23 during Month 1 and at Day 1 (pre-dose) and at Day 8 monthly until dose stabilization is achieved. Once maintenance dosing is achieved, PK/PD samples will be collected quarterly at Day 1 and Day 8 in the first year and then every 6 months thereafter.

Immunogenicity

Immunogenicity will be assessed by measuring anti-somavaratan antibodies (anti-drug antibodies, ADAs) at baseline and every three months during the first year of this study and then every 6 months thereafter. Testing will follow a tiered approach consisting of screening, confirmation, titration and additional characterization of confirmed positive ADA samples.

Study Population

The study population will consist of adults age 18-75 who have well-established growth hormone deficiency (GHD). Eligible subjects will have completed a Versartis adult GHD study or will be included as new subjects who are either rhGH treatment naïve or transitioned from daily rhGH therapy to twice-monthly somavaratan. New subjects transitioning from daily rhGH therapy must discontinue daily rhGH use for a minimum of 14 days prior to somavaratan dosing. Dosing will be stratified by 2 cohorts (Cohort 1: adults with GHD irrespective of age and gender; Cohort 2: women receiving oral estrogen).

CRITERIA FOR INCLUSION AND EXCLUSION

Inclusion Criteria:

1. Female or male subjects, between 18 and 75 years (inclusive) of age, with the diagnosis of AGHD
2. Eligible subjects may be naïve to somavaratan or have previously received somavaratan in the setting of a prior Versartis study
 - Subjects naïve to somavaratan must have a documented medical history of GHD during adulthood according to the Endocrine Society guidelines¹⁴ (confirmatory testing should be done to document persistence of childhood onset GHD into adulthood if necessary).
 - Subjects who have previously received somavaratan in the setting of a prior Versartis study can be included in this study if they have not met a stopping criterion in the corresponding study and somavaratan was well tolerated as judged by the Investigator and the Medical Monitor.
3. Naïve subjects must have an IGF-I SDS value ≤ 0 at Screening
4. All subjects must agree to the contraceptive requirements outlined in Appendix 2, if applicable.
5. Female subjects of childbearing potential must have a negative pregnancy test at Screening and before Dose 1.
6. Naïve subjects who are taking any other hormone replacement therapy must have been on a stable course of treatment for at least 3 months prior to Screening (routine dose adjustments are acceptable). Subjects transitioning from other Versartis adult GHD studies and who are receiving other hormone replacement therapy may have experienced dose adjustments or initiation of treatment during their previous study and may continue treatment per standard clinical practice.
7. Naïve to somavaratan subjects currently receiving daily rhGH injections for treatment of GHD, must agree to stop taking prescribed daily rhGH therapy for the washout period of ≥ 14 days.
8. Underlying disorders responsible for the subject's GHD must have been clinically stable for at least 6 months prior to Screening.
9. Subjects must provide written informed consent.
10. Subjects must have a BMI (kg/m^2) between 18.0 and 40.0 (inclusive).

Exclusion Criteria:

1. Subjects with untreated adrenal insufficiency or unknown adrenal function.
Prior Versartis study subjects will have been previously screened, however new subjects will require documentation of adrenal function via adrenal stimulation test prior to treatment. New subjects must have had an adrenal stimulation test within 3

months prior to treatment with somavaratan. Adrenal stimulation tests (as well as repeat/follow-up testing in at-risk patients) will be performed per institutional protocol.

2. Subjects with recently diagnosed thyroid dysfunction who have not started treatment or have not been stable on therapy for at least 3 months.
3. Subjects currently taking anti-inflammatory dose of glucocorticoids that could potentially compromise safety or efficacy assessments
4. Subjects currently receiving any GHRH or IGF-I product
5. Subjects with current significant cardiovascular disease, heart insufficiency of NYHA class > 2.
6. Subjects with significant comorbidities thought to increase risk of receiving growth hormone treatment or confound assessment of study outcomes (e.g. hepatic or inflammatory disorders that may affect GH-mediated hepatic IGF-I production or renal disorders that may alter somavaratan PK).
7. Subjects with a documented history of diabetes mellitus or inadequate glucose control as defined by a historical or Screening value of: FPG > 126 mg/dL (7 mM), or HbA1c \geq 6.5%
8. Subjects with current papilledema
9. Subjects with current drug or alcohol abuse.
10. Subjects with a documented history of HIV, current HBV or HCV infection (testing not required).
11. Subjects with a history of malignancy in adulthood (subjects with a history of childhood malignancy that were subsequently treated with rhGH in childhood and remain GHD in adulthood may be enrolled).
12. Women who are pregnant or breastfeeding.
13. Subjects treated with an investigational drug other than somavaratan within 30 days prior to Screening.
14. Subjects with a significant abnormality in Screening test results as interpreted by the Investigator and/or the Medical Monitor.
15. Impossibility of or unwillingness to participate in all trial activities.

TEST PRODUCT, DOSE, AND MODE OF ADMINISTRATION

Somavaratan will be administered as subcutaneous injection(s) in the thigh, abdomen, upper arm or buttocks. Administration of injections will be rotated to different injection sites. Study drug may be administered by trained subjects/caregivers, or a health care professional.

A subject will be considered to have achieved a maintenance stable dose when two consecutive 7 days post-dose (Day 8, peak) IGF-I SDS values are between 0 and 2.0 SDS. Subsequently, the subject will continue to receive the maintenance dose twice-monthly (every

15 days \pm 2 days). Maintenance doses may be adjusted further at the discretion of the Investigator or Medical Monitor while keeping IGF-I at 7 days post-dose between 0 and 2.0 SDS.

If a subject on a maintenance dose has an IGF-I SDS value above 2.0 SDS, dose adjustments shall be made by the Investigator or Medical Monitor based on clinical judgment with the objective to achieve and maintain IGF-I at day 7 post-dose between 0 and 2.0 SDS

The starting doses (Table 1) and Dose Titration Plan (Table 2) may be altered based on evaluation of the Phase 2 data, or ongoing evaluation of data gathered during this study. Adjustments may be implemented to alleviate safety concerns or optimize normalization of IGF-I SDS responses. The Investigator and Medical Monitor may agree to temporarily alter or suspend a subject's dose during illness or injury.

Table 1 Study Drug Starting Dose Information:

Subject Cohort Assignment	Fixed Starting Study Dose	Frequency of Administration
Cohort 1: Adults with GHD irrespective of age and gender	20 mg	Twice-Monthly
Cohort 2: Women receiving oral estrogens	40 mg	Twice-Monthly

Table 2 Dose Titration Plan

Downward Dose Titration		
IGF-I at Day 8	Cohort 1	Cohort 2
0 to 2.0 SDS	No change in dosing	No change in dosing
2.01 to 3.0 SDS	4 mg dose decrement	4 mg dose decrement
Greater than 3.0 SDS	10 mg dose decrement	10 mg dose decrement
Upward Dose Titration ¹		
IGF-I at Day 8	Cohort 1	Cohort 2
-1.0 to 0 SDS	4 mg dose increment	10 mg dose increment
Less than -1.0 to -2.0 SDS	10 mg dose increment	20 mg dose increment
Less than -2.0 SDS	20 mg dose increment	40 mg dose increment

1: Maximum allowable dose is 250.0 mg

DURATION OF TREATMENT

Subjects may continue on somavaratan treatment until the product is commercially available in their country or until the study is discontinued by the sponsor.

CRITERIA FOR EVALUATION – SAFETY

The following evaluations will be performed to assess study eligibility and safety:

1. Physical examination including injection site(s) evaluation.
2. Vital signs including sitting blood pressure, pulse rate, temperature and respiratory rate.
3. Laboratory tests: IGF-I, complete blood count, chemistry, fasting plasma glucose and insulin, hemoglobin A1c, thyroid function tests (Free T4 and TSH), pregnancy testing (for women of childbearing potential), lipid profile, ECGs (new subjects only), and screening anti-drug antibodies (ADAs).
4. Adverse events (AEs)
5. Concomitant medications (CMs)

Safety monitoring will continue up to approximately 60 days after a subject's final dose of somavaratan.

CRITERIA FOR EVALUATION – PHARMACODYNAMICS

Pharmacodynamic (PD) parameters include values of IGF-I and IGFBP-3. During month 1 of treatment, subjects will have IGF-I and IGFBP-3 measured every week (Day 1, Day 8, Day 16 and Day 23). After the first month and during the rest of the Titration Period, subjects will have IGF-I values measured at Day 1 (pre-dose, trough) and 7 days after dosing (Day 8, peak) of each month. During maintenance dosing PD parameters will be measured at Day 1 (pre-dose, trough) and 7 days after dosing (Day 8, peak) every three months for one year, and then every six months thereafter. Additional blood sample collection for IGF-I measures may be needed if previously stabilized subjects require further dose adjustments.

CRITERIA FOR EVALUATION – IMMUNOGENICITY

Immunogenicity will be assessed by screening for anti-drug antibodies (ADAs) at baseline and every 3 months during the first year and every 6 months thereafter. ADAs will be measured on blood samples collected at troughs (pre-dose). Testing will follow a tiered approach consisting of screening, confirmation, titration, and additional characterization of confirmed ADA positive samples.

STATISTICAL METHODS

Safety data will be listed by subject and summarized by cohort using frequencies or descriptive statistics. All subjects who receive at least one dose of somavaratan will be included in the safety analysis. Summaries of all adverse events (AEs), serious adverse events (SAEs), and incidence of Grade 3 or 4 adverse events will be classified according to severity and relationship to study drug.

No formal hypothesis testing is planned for this extension study.

For continuous variables, descriptive statistics will include the number of subjects, mean, standard deviation (SD), median, minimum, and maximum. For categorical variables, descriptive statistics will include the number and percentage of subjects in each category.

Summaries of subject disposition, demographics, disease characteristics, and exposure and response to dosing of study medication will be provided.

Somavaratan ADAs will be summarized descriptively.

AEs, PK, and PD will also be descriptively summarized by ADA subgroup (positive, negative) to assess potential effects of ADA positivity.

TABLE OF CONTENTS

APPROVAL/SIGNATURE PAGE: SPONSOR AND CONTRACT RESEARCH ORGANIZATION	2
SYNOPSIS: PROTOCOL 15VR8.....	3
LIST OF ABBREVIATIONS AND DEFINITIONS OF TERMS.....	15
1 INTRODUCTION	22
1.1.1 Adult Growth Hormone Deficiency.....	23
1.1.2 Pediatric Growth Hormone Deficiency	24
1.1.3 Summary of Clinical Experience	26
2 STUDY OBJECTIVES.....	28
2.1 Primary Objective.....	28
2.2 Secondary Objectives.....	28
3 INVESTIGATIONAL PLAN.....	29
3.1 Overall Study Design and Plan.....	29
3.2 Rationale for Study Design.....	31
3.3 Dose Selection	31
3.4 Study Duration and Dates.....	32
3.5 Safety Review and Stopping Rules.....	32
3.5.1 Stopping Rules.....	32
STUDY POPULATION SELECTION	33
3.6 Study Population.....	33
3.7 Inclusion Criteria:	33
3.8 Exclusion Criteria:	34
3.9 Subject Withdrawals and Replacements.....	35
4 STUDY TREATMENT(S).....	36
4.1 Description of Treatment(s).....	36
4.1.1 Somavaratan Treatment	36
4.2 Treatments Administered.....	36
4.3 Selection and Timing of Dose for Each Subject.....	37

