Immunogenicity was assessed at 4 time points in Phase 1b, at three time points in Phase 2a, and at 3 time points in the Extension Study in all pediatric subjects enrolled in these two studies by measuring anti-somavaratan antibodies (anti-drug antibodies, ADA) in serum samples. The serum from all ADA-positive subjects was further characterized using an *in vitro* cell assay that determines if the serum sample can inhibit human growth hormone (hGH) stimulated cell proliferation.

ADAs were first observed at Month 3 and remained consistent at Months 6, 12 and 18. Analyses have been performed on Month 18 data to determine if ADA positive and negative subjects differed with respect to clinical endpoints. ADA status had no statistically significant effect on the incidence or type of related adverse events, height velocity, drug concentrations, IGF-I responses or IGFBP-3 responses. The serum from several ADA-positive subjects tested positive for the ability to inhibit hGH in an *in vitro* cell proliferation assay. However, there were too few subjects that showed *in vitro* cell inhibition to conduct meaningful analysis of the significance of these results on clinical endpoints.

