3.4 Study Duration and Dates

This study is a long-term evaluation of somavaratan administered twice-monthly. Subjects may continue on somavaratan treatment until the product is commercially available in their country or until the study is discontinued by the sponsor.

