3.5.1 Stopping Rules

The Stopping Criteria include:

1. The Principal Investigator (PI) and/or Medical Monitor conclude it is unsafe or not in the subject's best interest to continue.
2. IGF-I SDS \geq 3.0 SDS on two consecutive Day 8 time points despite dose adjustments
3. IGF-I SDS \geq 2.0 SDS on two consecutive Day 8 time points despite dose adjustments and accompanied by clinically meaningful drug-related AEs, as determined by the Investigator and the Medical Monitor.

Subjects meeting individual stopping criteria will be withdrawn from the study.

The Stopping Criteria for a dosing cohort or the study include the determination that the dosing cohort or the study is unsafe to continue.

STUDY POPULATION SELECTION

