11. PD samples include IGF-I and IGFBP-3, collected on Day 1, 8, 16, and 23 in the first month, on Day 1 and 8 during monthly titration, and on Day 1 and 8 at all quarterly visits during the first year and every 6 months thereafter. In new naïve to somavaratan subjects only, a PD sample is required at Screening.
12. Serum samples will be collected for anti-somavaratan antibodies (ADAs). Samples are to be collected at Screening and pre dose at each quarterly visit (Day 1, M3, M6, M9, and M12) during the first year and every 6 months in subsequent years (e.g., M18, M24, M30, etc.). New subjects naïve to somavaratan treatment require an additional ADA sample collected pre-dose at M1.
13. Complete blood count and differential. Samples are to be collected at Screening and pre-dose at each quarterly visit (Day 1, M3, M6, M9, and M12) during the first year and every 6 months in subsequent years (e.g., M18, M24, M30, etc.).
14. Includes ALT, AST, GGT, phosphate, alkaline phosphatase, bilirubin, glucose, calcium, albumin, total protein, potassium, sodium, BUN and creatinine. Samples are to be collected at Screening and pre-dose at each quarterly visit (Day 1, M3, M6, M9, and M12) during the first year and every 6 months in subsequent years (e.g., M18, M24, M30, etc.).
15. Includes fasting cholesterol, HDL, LDL, triglycerides, ratio of total/LDL cholesterol and hs-CRP. Samples are to be collected at Screening and pre-dose at each quarterly visit (Day 1, M3, M6, M9, and M12) during the first year and every 6 months in subsequent years (e.g., M18, M24, M30, etc.).
16. Includes fasting insulin and glucose, HbA1c. Samples are to be collected at Screening and pre-dose at each quarterly visit (Day 1, M3, M6, M9, and M12) during the first year and every 6 months in subsequent years (e.g., M18, M24, M30, etc.).
17. Includes Free T4, TSH. Samples are to be collected at Screening and pre-dose at each quarterly visit (Day 1, M3, M6, M9, and M12) during the first year and every 6 months in subsequent years (e.g., M18, M24, M30, etc.).
18. ACTH stimulation test to be performed locally (within 3 months of screening visit) according to institutional protocol (not required for subjects with a documented history of adrenal insufficiency and who are taking glucocorticoid replacement therapy). Additional ACTH stimulation testing/adrenal function tests may be performed at the discretion of the Investigator per routine clinical practice.

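### The ADA-positive versus ADA-negative summaries have no status rule and no exposure adjustment, so AE percentages may partly reflect follow-up, pre-conversion events and prior exposure

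*Combined protocol and SAP*

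**What the plan says.** The Statistical Methods part of the synopsis plans this comparison: "AEs, PK, and PD will also be descriptively summarized by ADA subgroup (positive, negative) to assess potential effects of ADA positivity". No definition of positive or negative follows. Section 8.4 says only that ADAs are summarised descriptively and does not repeat the subgroup comparison.

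The features that bear on it are these.

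- **Summary measure.** Under Section 8.1 categorical variables are given as counts and percentages of subjects. No person-time rate, landmark, or rule about events before and after positivity is stated.
- **Layout.** Summaries are by cohort, that is, by oral estrogen use, and not by somavaratan-naive versus rollover.
- **Follow-up.** Section 3.4: "Subjects may continue on somavaratan treatment until the product is commercially available in their country or until the study is discontinued by the sponsor". Section 3.5.1: "Subjects meeting individual stopping criteria will be withdrawn from the study".
- **ADA sampling.** The synopsis has it "at baseline and every 3 months during the first year and every 6 months thereafter". Appendix 1 adds: "New subjects naïve to somavaratan treatment require an additional ADA sample collected pre-dose at M1".
- **Timing of ADAs.** Section 1.1.2: "ADAs were first observed at Month 3 and remained consistent at Months 6, 12 and 18". These are pediatric data, collected in part "at 3 time points in the Extension Study in all pediatric subjects enrolled in these two studies". No adult figure is given.
- **Population.** "A total of up to 250 subjects will be enrolled", of whom about 40 are to be new. The others come from earlier somavaratan studies, and Section 8.1 takes Baseline as the last value before the first dose in this study.

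**The concern.** A subject can be labelled positive only after staying long enough to convert and be sampled. If the label then covers the whole of that subject's time on study, three things follow. Short-stay subjects collect in the negative group. AEs before the first positive sample count for the positive group. Positives have, on average, longer to accumulate a first AE. Prior exposure adds a second route: a rollover may already be positive at Day 1, whereas new subjects pass through the introduction of treatment while probably still negative. Section 5.7.5 describes the related AEs as similar to those seen when rhGH is introduced.

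This is the only planned look at the clinical consequences of ADAs, and it supports a secondary objective. Its stated purpose is to assess effects of positivity, so a reader will take a difference between the columns as evidence about ADAs. A spurious difference could be read as harm, or could hide a real effect.

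**Working it through.** **No figure to reproduce.** The documents give no expected ADA rate, AE rate or power for this comparison, and 250 is an enrolment cap. The check asks what the table would show if ADAs had no effect at all. AE rates, conversion rates and follow-up distributions below are assumptions.

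**Step 1, by hand.** Assume a constant AE rate λ = 0.05 per month, follow-up uniform over 1 to 36 months, and 30% of subjects converting, all at Month 3. For follow-up uniform on (a, b),

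P(any AE) = 1 − [exp(−λa) − exp(−λb)] / [λ(b − a)].

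- Ever-positive subjects have follow-up on (3, 36): 1 − (0.8607 − 0.1653)/1.65 = 57.9%, mean follow-up 19.5 months.
- Non-converters, on (1, 36): 1 − (0.9512 − 0.1653)/1.75 = 55.1%.
- Would-be converters who leave before Month 3, on (1, 3): 1 − (0.9512 − 0.8607)/0.10 = 9.5%. Their weight is 0.30 × 2/35 = 0.017, against 0.70 for non-converters.
- Never-positive overall: (0.70 × 55.1% + 0.017 × 9.5%)/0.717 = 54.0%, mean follow-up 18.1 months.

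The false gap is 3.9 points, and 3/19.5 = 15% of the AEs in positives precede the first positive sample. If everyone stays 12 to 36 months, both groups give 1 − (0.5488 − 0.1653)/1.20 = 68.0%, and the gap is zero.

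**Step 2, later conversion (simulation, 400,000 subjects per scenario).** Let conversion continue after Month 3 at a constant monthly rate, detected at the next scheduled sample, with the same λ.

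| Conversion per month | Follow-up (months) | Any AE, ever-positive v never-positive | Gap (points) |
|---|---|---|---|
| 0.01 | 1–36 | 69.4% v 53.2% | 16.2 |
| 0.02 | 1–36 | 69.1% v 51.2% | 17.9 |
| 0.05 | 1–36 | 68.0% v 45.5% | 22.5 |
| 0.02 | 12–36 | 71.4% v 66.7% | 4.7 |

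At 0.02 per month with follow-up of 1–36 months, mean follow-up is 25.0 v 16.7 months, and 56% of AEs in positives precede the first positive sample.

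**Step 3, allowing for rollovers.** If the cap is filled with 40 new subjects, rollovers are 210/250 = 84%. Assume their status is settled at Day 1. For the rest, conversion is either all at Month 3 or spread over Months 3/6/9/12 as 55/25/10/10%. The grid is 30% or 60% converting, 0.5 to 2 AEs per person-year, and follow-up uniform from 1 to 12 or 24 months.

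| Rollovers | False gap (points) | Share of positives' first AEs before conversion |
|---|---|---|
| 0% | about 4 to 16 | 28–65% |
| 50% | about 2 to 7 | 14–28% |
| 84% | about 0.5 to 2.6 | 4–9% |

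**Step 4, does time-linked status remove it?** With a constant AE rate, events per person-month are 0.050 in positive time and 0.050 in negative time in every scenario. If AEs in naive subjects are 2 to 3 times more frequent in the first 3 months (half rollovers, 20% of them positive at Day 1), rates still differ: 0.050 v 0.055–0.061. Person-time alone is not enough when AEs cluster early.

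**The case against.** **Subject-level status is not stated.** This stands. The synopsis says only positive and negative. But a percentage-of-subjects table needs one label per subject, and Section 1.1.2 describes the sponsor's pediatric analysis as a comparison of positive and negative subjects. It is the natural reading, not a written rule.

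**Details are deferred to an SAP.** Sections 8.1 and 9.10 say so, and the supplied text holds no such detail. That makes this the place to set the rule. It does not show that a sound rule exists.

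**The pediatric data point to a small bias.** Prevalence that is steady after Month 3 suggests early conversion, and a large rollover share shrinks the gap further. Both points stand and are why the lower figures must be shown. Stable prevalence need not mean that no individual converted later, and no adult timing is given.

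**PK and PD are measured at scheduled visits.** The follow-up argument does fit AE percentages best. For PK and PD a subject-level label would still assign pre-conversion values to the positive group, and sampling is densest in Month 1. For IGF-I there is a further difficulty: Section 3.1 titrates dose to an IGF-I target of 0 to 2.0 SDS, which can mask an ADA effect.

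**The comparison is descriptive and untested.** True, which limits the stakes. The stated purpose is still to assess an effect.

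A reader might infer that the table measures follow-up and prior exposure instead of any ADA effect. The documents do not support that: the amount of confounding cannot be fixed from them, and under some plausible inputs it is nil.

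**Conclusion.** The concern holds in a limited form. ADA status is undefined, and nothing stated adjusts for person-time, timing of positivity or rollover status. Read as one label per subject, AE percentages by ADA status may partly reflect how long subjects stayed, events before conversion, and earlier exposure.

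With no true ADA effect, the false gap is:

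- about 0.5 to 3 points with 84% rollovers settled at Day 1;
- about 2 to 7 points with 50% rollovers;
- about 4 to 16 points if all conversion is on study at Month 3 or later and follow-up runs from 1 to 12 or 24 months;
- up to about 23 points with continuing late conversion and follow-up to 36 months;
- zero if all conversion is at Month 3 and everyone stays at least 12 months.

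Late conversion among rollovers would raise the first two ranges, but the documents give no rate for it. The point merits a change because a better method is available at little cost, not because a large bias has been shown.

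**What to change.** Write the following into the SAP.

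1. Define ADA status as time-varying. Assign each AE to positive or negative time by the most recent ADA result at onset, and report events per person-time.
2. Show this separately for somavaratan-naive and rollover subjects, and by time on drug (for example first 3 months versus later). Step 4 of the working shows why person-time alone does not suffice.
3. Summarise PK and IGF-I/IGFBP-3 by the ADA result of the same visit, with the concurrent dose alongside.
4. Keep a subject-level ever-positive table as a supplement, labelled as unadjusted for follow-up.

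The cost is wording and programming. ADA, PK and PD samples are already scheduled together at Day 1 and the quarterly visits of the first year, then every 6 months, so no new samples are needed. The downside is that conversion is dated only to the 3- or 6-month sampling grid, so some time after true conversion will be counted as negative. An AE shortly before a first positive sample cannot be ruled out as ADA-related, and the table should say so.
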